#### **4.6 Efficacy Analyses**

All efficacy analyses will be conducted by treatment for the ITT Population. Selected analyses may be conducted in the PP and RE Populations. Endpoints involving response assessment will be based on central radiology per mRECIST 1.1. Investigator assessment per mRECIST 1.1, or central radiology assessment per Choi criteria will only be used supportively.

##### **4.6.1 Multiplicity**

A gate-keeping method will be implemented to control Type I error. This strategy will apply to the primary and key secondary efficacy endpoints: PFS, ORR, and OS.

PFS will be analyzed first when approximately 264 events are reached. In line with the gate keeping strategy, ORR will only be assessed for superiority should PFS have demonstrated superiority.

A formal OS interim analysis will be performed at the time of the final analysis of PFS and ORR for which superiority is demonstrated. The alpha for the interim analysis of the OS will follow the O'Brien-Fleming boundary method. The amount of alpha spent on OS at the time of the final PFS analysis will be specified according to the actual proportion of deaths observed at the time of the database lock regardless of whether the exact targeted number of PFS events has occurred at the lock. The exact amount of alpha spending at the interim analysis will be calculated using the alpha spending function developed by Lan and DeMet. OS will be analyzed when superiority is demonstrated for both PFS and ORR. The OS will also be analyzed at the follow-up when 264 events (deaths) occur, using the remaining unspent alpha.

##### **4.6.2 Analysis of Primary Efficacy Endpoint**

The primary endpoint of PFS is defined as the time from the date of randomization to the earlier of the date of first documented disease progression or death due to any cause.

The primary analysis for PFS is based on the central radiological assessment of PD per mRECIST 1.1.

Patients who are still in response at time of data cutoff will be censored at their last valid assessment. Complete censoring rules (both European Medicines Agency [EMA] and United States [US] Food and Drug Administration [FDA]) are specified in [Table 2](#). The analysis will be primarily based on FDA Guidance for Cancer Trial Endpoints ([FDA, 2007](#)). The

**Avapritinib**  
**Statistical Analysis Plan Study BLU-285-1303**

censoring rules based on the EMA Guideline on the evaluation of anticancer medicinal products in man will be used as a sensitivity analysis ([EMA, 2017](#)).

The Kaplan-Meier (KM) method will be used to estimate the survival distribution function. The median PFS and its two-sided 95% CI and the 25th and 75th percentiles will be estimated. In addition, the event rates (or event-free) at specific time-points (e.g., 3-, 6-, and 12-month, *etc.*) will be computed, along with their standard errors using Greenwood's formula ([Klein, 2003](#)). Plots of survival curves by treatment using the KM method will be presented. Additional survival plots will be provided by treatment for each of the three stratification factors (defined in [Section 3.1](#)).

The primary treatment comparison is based on a stratified log-rank test.

The hazard ratio (HR) and its 95% CI will be estimated based on a stratified Cox model with treatment as the explanatory variable and strata for the stratification factors.

If patients were randomized based on incorrect strata, then the corrected strata will be used for stratified analyses rather than the incorrect strata recorded at randomization.

As a sensitivity analysis, the stratified analyses of PFS based on the central radiological assessment of PD per mRECIST 1.1 will be repeated for the PP Population. Unstratified analyses based on the ITT population may also be conducted.

PFS derived from the Investigator's assessment per mRECIST 1.1 will be used as a supportive analysis of the primary endpoint.

**Avapritinib  
Statistical Analysis Plan Study BLU-285-1303**

**Table 2: Progression Free Survival Censoring Rules**

Situation	Date of Progression or Censoring	FDA Censoring Rules	EMA Censoring Rules
No baseline assessments and alive after 2 scheduled assessments (defined by 130 days)	Date of randomization	Censored	Censored
Progression documented between scheduled visits	Date of radiological assessment showing new lesions or an increase in measured lesions	Event	Event
No progression	Date of last radiological assessment with evidence of no progression (or randomization date if no assessment)	Censored	Censored
New anticancer/ non-protocol treatment started prior to progression	Date of last radiological assessment with evidence of no progression prior to the start of new anticancer treatment	Censored	Event at date of disease progression/death
Death before the second scheduled post-baseline assessment (defined by within 130 days of date of randomization)	Date of death	Event	Event
Death between scheduled assessments	Date of death	Event	Event
Death or progression immediately after an extended lost to follow-up time (2 more missed scheduled assessments defined by at least x  days)	Date of last radiological assessment with evidence of no progression (randomization date if first 2 scheduled assessments are missing)	Censored	Event at date of disease progression/death

 x = 130 days if the death or progression date is ≤336 days from first dose date; x = 210 days if the death or progression date is ≥337 days from randomization date.

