All patients will attend an End-of-Treatment (EOT) visit within 14 ( $\pm$ 7) days after the last dose of study drug. A safety Follow-up visit for resolution of any ongoing AE will be made on Day 30 ( $\pm$ 7 days) after the last dose of study drug, or at the time the patient initiates another antineoplastic therapy. Patients who discontinue study treatment before disease progression will undergo tumor assessments every 8 weeks until disease progression, death, or patient withdrawal of consent. After documentation of disease progression by central radiology review, patients are to be followed for subsequent antineoplastic therapy and survival approximately every 2 months until death, withdrawal of consent or closure of the study by the Sponsor.

The expected enrollment period is approximately 18 months, and the expected duration of the study to reach the primary analysis timepoint is approximately 24 months until a total number of 264 PFS events are reached. The study will be completed when all patients are no longer receiving study drug and follow-up for OS has been concluded.

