## 7.8 End-of-Treatment, Safety Follow-up and Progression-Free Survival Follow-up

All patients will attend an EOT visit approximately 14 days ( $\pm$  7 days) after the last dose of study drug (see [Table 2](#) for a description of EOT assessments). If an alternative antineoplastic treatment is started within 14 days of the last dose of study drug, the EOT visit should be conducted before the first dose of the alternative antineoplastic therapy. Tumor assessment for EOT procedures do not need to be repeated if they were performed within 7 days (or within 28 days for disease response assessments).

A Safety Follow-up visit (clinic visit or a phone call) for resolution of any ongoing AE will be made 30 days ( $\pm$  7 days) after the last dose of study drug, or at the time the patient initiates another antineoplastic therapy.

Thereafter, patients without documented PD will be followed approximately every 8 weeks ( $\pm 7$  days) until disease progression, death, initiation of new anti-GIST therapy, withdrawal of consent, or closure of the study by the Sponsor.

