**1.2.3 Exploratory Objectives**

### **1.3 Sample Size Justification**

The sample size calculation was based upon the assumption that the median PFS for regorafenib is approximately 5 months (Demetri 2013). Assuming avapritinib can reduce the risk of PFS events by 33%, i.e., a hazard ratio (HR) of 0.67 (avapritinib compared to regorafenib), a minimum of 264 PFS events are needed to provide 90% power at a 2-sided alpha of 0.05 for the study. With an 18-month accrual period and a 6-month follow-up period, the total sample size needed for the study is approximately 460 patients (230 patients per arm). This sample size takes a 2% dropout rate into consideration and assumes accrual will follow a truncated exponential distribution with a scaled power parameter of -9.

The sample size calculated for the primary endpoint, PFS, is also sufficient to detect a difference in ORR between the two arms. Assuming a null ORR of 5% and an alternative ORR of 15%, a sample size of 460 patients provides approximately 95% power to detect a difference in ORR using a test of two-proportions at a 2-sided alpha of 0.05.

Assuming the same effect size for OS as PFS (HR = 0.67), the same number of events (264) is required to power the OS analysis. The timing of the OS analysis will occur later than the PFS analysis as it will be at such time when 264 deaths occur.

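### The protocol contradicts itself on tumor imaging after new anti-GIST therapy; where imaging stops, the SAP's EMA sensitivity analysis of PFS lacks the progression dates it needs

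*SAP*

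**What the plan says.** Here a switch means starting non-protocol anticancer therapy before centrally documented progression. Crossover to avapritinib requires central progression, so it is not a switch in this sense.

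**Imaging ends at a switch.** Protocol 7.8 follows patients without documented progression "until disease progression, death, initiation of new anti-GIST therapy, withdrawal of consent, or closure of the study by the Sponsor". The same list of stopping reasons stands in Section 6.1, in note g of the schedule of assessments (Protocol Table 2), and in the Study Summary under Duration of Patient Participation.

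**Imaging continues.** Protocol 4.1 says: "Patients who discontinue study treatment before disease progression will undergo tumor assessments every 8 weeks until disease progression, death, or patient withdrawal of consent". The Study Design part of the Study Summary agrees. Both also keep the 8-week schedule running after treatment is stopped for whatever reason, until central review confirms progression. Section 7.5.1 and schedule note t run it to progression or death. None of these places names new therapy as a reason to stop.

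**The SAP.** In SAP Table 2, the row "New anticancer/ non-protocol treatment started prior to progression" censors at the last progression-free scan before the new treatment under the FDA rule, and counts an event at progression or death under the EMA rule. SAP 4.6.2 makes the FDA rule primary and the EMA rule a sensitivity analysis. The other planned PFS analyses are per-protocol, optional unstratified and investigator-assessed (SAP 4.6.2), and Choi-based (Protocol 10.5.3.1).

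**Survival contact.** Section 6.1 lets survival follow-up begin once imaging ends. Section 7.9, schedule note h and Section 4.1 start it after centrally documented progression.

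**The concern.** Censoring at a switch is informative if patients switch because they are about to progress. The usual check is to ignore the switch and use the later progression date, which is what the EMA column does. If a site follows Section 6.1, Section 7.8 or note g, that date is not collected. The patient then enters the EMA analysis only through death, which comes later than the unseen progression, or has no event.

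What is at stake is false reassurance. If switching is unequal, the sensitivity analysis can repeat the distortion of the primary analysis, and agreement between the two would look like robustness. Duration of response inherits the problem, because SAP 4.6.3.3 applies the same table.

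**Working it through.** **1. The plan's own figures.** SAP 1.3 states that "a minimum of 264 PFS events are needed to provide 90% power at a 2-sided alpha of 0.05 for the study", at HR 0.67, and that "the median PFS for regorafenib is approximately 5 months".

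- Schoenfeld: 4 × (1.960 + 1.282)² / (ln 0.67)² = 262.06, so 263 events. Freedman's formula gives 270. Power with 264 events is 90.2%.
- Sample size ("With an 18-month accrual period and a 6-month follow-up period"): monthly hazards are ln 2 / 5 = 0.1386 and 0.67 × 0.1386 = 0.0929. Entry density is proportional to exp(0.5u) on 0 to 18 months (scaled parameter −9, and 9/18 = 0.5). The probability of an event by month 24, averaged over entry times and arms, is 0.588. Then 264 / 0.588 = 449, and 449 / 0.98 = 458 against the stated 460.

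The stated figures reproduce. The point rests on conflicting text, not on arithmetic.

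**2. What depends on scans after a switch.**

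| PFS analysis | Changes the new-therapy rule? | Needs post-switch scans for that rule? |
|---|---|---|
| Primary, FDA censoring | – | No; it stops at the last scan before the switch |
| EMA sensitivity | Yes | Yes, unless the patient dies |
| Per-protocol, unstratified | No | No |
| Investigator, Choi | No | No; same imaging schedule |

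**3. Number of patients.** The documents give no switching rate, so shares of 2% to 15% per arm are assumed. Equal shares of 2%, 5% and 10% of 460 are 9, 23 and 46 patients. With 15% in one arm and 5% in the other, 230 × 0.15 + 230 × 0.05 = 46.

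**4. Illustration.** The assumptions are:

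- exponential PFS as in step 1, 230 patients per arm, analysis at month 24;
- a switch at a uniformly distributed 60% to 100% of the patient's own time to progression, which the new therapy does not alter;
- death after progression only, with a median gap of 8 months;
- unstratified Cox model, 400 simulated trials per row and data treatment.

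Cells show the HR, with mean events in parentheses. Shares are regorafenib / avapritinib.

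| Switching | Scans continue | FDA rule | EMA, scans stop, living censored at cutoff | EMA, scans stop, living censored at last scan |
|---|---|---|---|---|
| 2% / 2% | 0.668 (270) | 0.668 (265) | 0.677 (266) | 0.667 (266) |
| 5% / 5% | 0.672 (271) | 0.669 (258) | 0.670 (262) | 0.665 (262) |
| 10% / 10% | 0.673 (271) | 0.674 (244) | 0.676 (252) | 0.670 (252) |
| 15% / 5% | 0.661 (270) | 0.736 (241) | 0.772 (252) | 0.718 (251) |
| 5% / 15% | 0.674 (271) | 0.605 (246) | 0.607 (253) | 0.617 (254) |

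Simulation error is about 0.67 × (2/√270)/√400 = 0.004 in the HR, so the spread in the second column is noise.

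With equal switching, the EMA analysis without later scans loses 270 − 266 = 4, 271 − 262 = 9 and 271 − 252 = 19 events, and the HR stays near 0.67. With unequal switching it lands close to the FDA result and away from 0.67, whereas continued scans recover 0.67 within simulation error.

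**The case against.** Several stronger readings are tempting, and the documents do not support them.

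- *The EMA analysis cannot be carried out.* It can. Its rule accepts death, Section 6.1 provides for survival follow-up after imaging ends, and the EMA row for missed assessments does not depend on post-switch scans.
- *Progression after a switch is never seen.* Several protocol sections require the scans, and a site following them will supply the dates. Section 7.8 itself does not mention scans. But Section 6.1 and note g do, and note g governs the PFS follow-up column of the schedule, so stopping remains a compliant reading.
- *The EMA analysis is the only check on the primary result.* Others are planned, and investigator-assessed PFS can partly probe censoring that arises from local and central disagreement. None of them changes the new-therapy rule or supplies the missing scans.
- *Regorafenib patients will switch more because crossover needs central progression.* This is conjecture. Section 7.5.1 bars stopping treatment for local progression before central confirmation, Section 6.3.1 allows interruptions of up to 56 days, and the prospect of crossover is a reason to stay until central progression. On the other side, the trial is open-label, and SAP 4.2 lists clinical progression apart from centrally confirmed progression as a reason for stopping. Neither argument settles the rate. The nearest figure is from phase 1 (Protocol 1.2.3.1): (6 + 3)/116 = 7.8% had stopped for adverse events or by their own decision. Those data were immature, cover avapritinib only, and do not show who started new therapy.
- *The gap favors avapritinib.* If the regorafenib arm switches more, the HR moves toward 1, against avapritinib. Only the reverse pattern favors it.

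It also stands that only a sensitivity analysis is touched.

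**Conclusion.** The contradiction in the protocol is certain. So is its link to the SAP: the one planned PFS analysis that changes the new-therapy censoring rule needs progression dates that four protocol places allow sites not to collect. Where those places are followed, the analysis is incomplete and does not correct informative censoring when switching differs between arms.

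The size is conditional. Under the stated assumptions, equal switching of 2% to 10% costs about 4 to 19 of about 270 events and barely moves the HR. Switching of 15% against 5% moves a true 0.67 to 0.72–0.77 or to 0.61–0.62, depending on which arm switches more. These figures assume that switching anticipates progression, and the rates are assumptions, not trial data. The documents support no claim about the direction of bias in this trial. The primary FDA analysis, the 264 events and the 460 patients do not change.

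**What to change.** 1. In the Study Summary (Duration of Patient Participation), Section 6.1, Section 7.8 and schedule note g, remove the start of new anti-GIST therapy as a reason to end PFS imaging, so that they match Sections 4.1 and 7.5.1 and note t.
2. In SAP Table 2, state how the EMA analysis handles a switched patient with no later scan: for example, an event at death, and censoring at the last scan if alive with no recorded progression.
3. Extend the survival follow-up in Section 7.9 and schedule note h, and the matching sentence in Section 4.1, to patients who leave imaging without central progression.

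FDA censoring can stay primary. The cost is wording in both documents, plus some scans after new therapy that Sections 4.1 and 7.5.1 already require. The change is worth making early, because scans that were not taken cannot be recovered.

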### 10.5.3 Efficacy Analysis

#### 10.5.3.1 Analysis of the Primary Efficacy Endpoint

The primary endpoint of PFS is defined as the time from randomization to disease progression or death due to any cause, whichever occurs first. The primary analysis for PFS is based on the central radiological assessment of PD per mRECIST, version 1.1 in the ITT population.

Patients without disease progression or death at the time of analysis will be censored at their last date of tumor evaluation. Patients who withdraw from the study and receive subsequent antineoplastic therapy without documented PD will be censored at the time of the last adequate (CT or MRI scan available) disease assessment. For PD documented between scheduled evaluations, the actual date of PD will be used, not the date of the next scheduled evaluation. For death or PD after no more than 1 missed evaluation, the date of the event will be the date of PD or death, whichever occurs first. For death or PD after more than 1 missed evaluation, the date of the event will be censored at the last adequate disease assessment. Detailed censoring methods will be described in the statistical analysis plan (SAP).

The Kaplan-Meier method will be used to estimate the distribution of PFS for each treatment group. The primary treatment comparison is based on a stratified log-rank test in the ITT population. The HR, and its 95% CI, are to be estimated based on a stratified Cox's model with treatment as the explanatory variable. Stratification factors include TKI

treatment (third vs. fourth), geographic region (Asia vs. rest of the world), and mutation status measured in ctDNA or a tumor sample (PDGFR $\alpha$  D842V mutation present vs. absent).

Progression-free survival derived from the Investigator assessment per mRECIST, version 1.1 in the ITT population, and from central radiological assessment per Choi criteria in the ITT population will be evaluated and used as supportive evidence. The analysis of PFS based on the PP population will also be included as a sensitivity analysis.

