**6. CHANGES TO PLANNED ANALYSES FROM THE PROTOCOL**

There is no change to planned analyses from the protocol.

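### SAP Table 2, footnote 1: the missed-scan gap rises from 130 to 210 days at day 337 while imaging stays 8-weekly, so late PFS events that the protocol would censor are counted, and the footnote mixes two time origins

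*SAP*

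**What the plan says.** The protocol's rule for the primary endpoint (10.5.3.1) does not depend on time on study: "For death or PD after more than 1 missed evaluation, the date of the event will be censored at the last adequate disease assessment". It adds: "Detailed censoring methods will be described in the statistical analysis plan".

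The SAP turns this into a gap in days. The last row of Table 2 reads "Death or progression immediately after an extended lost to follow-up time (2 more missed scheduled assessments defined by at least x", with x in days; its FDA column, which drives the primary analysis (SAP 4.6.2), says censored. Footnote 1 then sets x in two limbs:

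- Early events, counted from first dose: "x = 130 days if the death or progression date is ≤336 days from first dose date".
- Late events, counted from randomization: "x = 210 days if the death or progression date is ≥337 days from randomization date".

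Two other rows of the table also equate two scheduled assessments with 130 days, without a time split: "No baseline assessments and alive after 2 scheduled assessments (defined by 130 days") and "Death before the second scheduled post-baseline assessment (defined by within 130 days of date of randomization").

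Protocol 4.1, 7.5.1 and Table 2 note t require imaging every 8 weeks (±1 week) from C1D1 until progression. Neither document lengthens the interval at any time. SAP Section 6 states: "There is no change to planned analyses from the protocol".

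**The concern.** A day threshold that stands for two missed scans has to follow from the scan interval. The interval does not change at day 337, but the threshold does. If 130 days is right early, 210 cannot be right later, and the same missed-scan history is censored on one side of the boundary and counted as an event on the other.

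The two limbs also start from different dates. If first dose falls after randomization, some dates satisfy both limbs. Randomized patients who were never dosed belong to the ITT population (SAP 2.1), but the 130-day limb has no starting date for them. A programmer would have to choose, and SAP 3.1 unblinds the study team at database lock. What is at stake is a primary-endpoint rule that contradicts the protocol and does not always give one answer.

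**Working it through.** **1. Gaps implied by the schedule.** Interval 56 days, window ±7 days at each scan. After m missed scans, the gap from the last post-baseline scan to progression at the next attended scan is 56(m+1) ± 14 days.

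| Missed scans | Gap (days) | x = 130 | x = 210 |
|---|---|---|---|
| 0 | 42-70 | event | event |
| 1 | 98-126 | event | event |
| 2 | 154-182 | censored | event |
| 3 | 210-238 | censored | censored |

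The 130-day figure reproduces the row's label, and any threshold from 127 to 154 would do the same for progression found at scheduled scans. The 210-day figure separates two misses from three. It would separate one from two at 11 weeks (140-168 vs 217-245), 12 weeks (154-182 vs 238-266) or 13 weeks (168-196 vs 259-287).

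**2. Example, in days from C1D1.** Last scan day 280; scans due on days 336 and 392 missed; progression on day 448. Gap 448 − 280 = 168, below 210, so the SAP counts an event. Protocol 10.5.3.1 censors at day 280.

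**3. Deaths.** If the last scan was 7 days early, the second missed scan's window closes 112 + 7 + 7 = 126 days after it. A death at 130-209 days therefore follows at least two missed scans, yet from day 337 it is an event.

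**4. Overlap of the limbs.** With L days from randomization to first dose, days 337 to 336 + L from randomization satisfy both limbs: 1 date at L = 1, 7 at L = 7, 14 at L = 14. At L = 0 there is none. The protocol does not require same-day dosing; 6.1 limits only the time from consent to dosing, to 28 days.

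**5. Patients with no post-baseline scan.** Here 130 days fails if the gap starts at the wrong date. A baseline scan may precede C1D1 by 28 days; with week 8 missed and progression at week 16 the gap is 28 + 112 = 140 after only one miss. Measured from randomization, the second scan's window closes at 112 + 7 + L = 119 + L days, which reaches 130 at L = 11.

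**6. How many events lie past day 337.** Inputs from SAP 1.3: 230 per arm, control median 5 months, HR 0.67 (5/0.67 = 7.46 months), 264 events, 18-month accrual with parameter −9. The event target reproduces: 4(1.960 + 1.282)²/(ln 0.67)² gives 263, and 264 events give power 0.902. Model: exponential PFS, dropout ignored, accrual density proportional to exp(9u/18), cut at 264 expected events, day 337 = 337/30.4375 = 11.07 months. Expected late events per arm are 230 × the mean of max(0, S(11.07) − S(T − u)) over entry times u, where T is the cut.

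| Accrual | Cut (month) | At risk past day 337 | Later events |
|---|---|---|---|
| Planned | 23.70 | 5.59 + 3.37 = 8.96 | 0.87 + 0.73 = 1.60 (0.6% of 264) |
| Uniform (assumption) | 18.01 | 31.72 + 19.11 = 50.83 | 8.34 + 6.84 = 15.18 |

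Avapritinib is given first in each sum.

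**7. How many are reclassified.** Miss rates are not in the documents. If each scan is missed independently with probability p, the chance that progression lies in an interval with exactly two missed scans is 3p²(1 − p)²: 0.0068 at p = 0.05 and 0.0768 at p = 0.20. Times 1.60 this is 0.01 and 0.12; times 15.18 it is 0.10 and 1.17. A simulation that places progression at the attended scan (lag 7 days, 10% of events deaths without progression; both assumptions) gives, for late events with a gap of 130-209 days:

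| Missed scans (assumption) | Planned accrual | Uniform accrual |
|---|---|---|
| 5%, independent | 0.02 | 0.2 |
| 20%, independent | 0.3 | 2.1 |
| 20% overall, 50% after a miss | 0.4 | 2.2 |

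Late events in the simulation are 2.7-4.4 (planned) and 21.5-26.4 (uniform). They exceed step 6 because detection waits for the next attended scan. Reclassified events divide about evenly between arms.

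**The case against.** The protocol hands detailed censoring methods to the SAP, so the SAP may set the day counts. That covers turning missed evaluations into days. It does not cover reversing the stated rule for late events, least of all while Section 6 reports no change.

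The effect is tiny, and the planned EMA-rule sensitivity analysis counts these events at their actual dates whatever x is, so the 210-day rule lies between a constant 130-day rule and the EMA rule. Both points stand and limit the weight of the finding. The larger figures need uniform accrual, which reaches 264 events at month 18.0 against the approximately 24 months planned.

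Three stronger readings are not supported:

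- A reader might infer that the footnote favors one arm or could change the result. The numbers in steps 6 and 7 are too small and too evenly divided for that.
- A reader might infer that progression at an on-time week-48 scan always falls under both limbs. The SAP counts days as difference plus one (3.2.3, 3.2.4), and its Table 1 formula puts week 48 at day 337 from first dose, outside the first limb. With no missed scan the gap is also about 56 days, so x is irrelevant.
- A reader might infer that 210 was carried over from a trial with 12-weekly scans. Intervals of 11 to 13 weeks fit equally well, and neither document contains one, so the origin is unknown.

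**Conclusion.** The footnote is wrong as written. From day 337 the primary FDA-rule analysis counts deaths and progressions with gaps of 130-209 days that protocol 10.5.3.1, the row's own label and the same table before day 337 would censor. The mixed origins give two answers for some dates and leave the first limb undefined for never-dosed patients. Duration of response uses the same table, but only descriptively (protocol 10.5.3.2.5).

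The contradiction rests on the text and the 8-week schedule alone. The size rests on exponential PFS, the planned accrual and assumed miss rates: about 0.02-0.4 of 264 events reclassified, or 0.2-2.2 if accrual were uniform. It should be corrected before database lock because the rule governs the primary endpoint, not because the result is likely to move.

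**What to change.** In footnote 1, delete the day-336/337 split and use x = 130 days for all events, measured from the last adequate post-baseline assessment.

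For patients with no post-baseline assessment, do not measure the gap from the baseline scan (step 5). Apply the rule by whether both of the first two scheduled scans, counted from C1D1 with their windows, were missed. Use randomization as the origin for never-dosed patients. Keep this consistent with the row that counts a death within 130 days of randomization as an event.

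If 210 days is intended, declare it in SAP Section 6 with a reason, use one time origin that exists for every ITT patient, and amend protocol 10.5.3.1.

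The first route costs one SAP footnote. Sample size, endpoint, test and data collection do not change. The second also needs a protocol amendment.
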